It is known that chronic hyperglycaemia causes increased risk of diabetic complications. It is possible that both glucose variability and postprandial hyperglycaemia are independent risk factors for this as well. There is some evidence that glucose variability and postprandial hyperglycaemic are common occurrence for children who have T1D. However, there is a paucity of published data on the prevalence of postprandial hyperglycaemia after breakfast in children and young people with T1D and no evidence-base for how to manage this phenomenon. The need for long-term studies to examine glucose variability from CGM data and, for closer examination of postprandial glucose variability to elucidate methods to reduce this, has been highlighted (Tansey *et al.* 2016). Although this applies to all meals, focusing on minimising postprandial hyperglycaemia after breakfast is paramount. This can help ensure good control through the morning and rest of the day when children are at school and actively learning (Tansey *et al.* 2016).

Aim:

To describe the distribution and dispersion of glucose variability and postprandial hyperglycaemia following breakfast, in children and young people with type 1 diabetes (T1D), using measurements from Dexcom CGM.

Objectives:

- To determine the glucose variability diurnally and nocturnally and in the four-hour postprandial breakfast period using measurement of 'time in range', 'time above range' and 'time below range'.
- To determine the variability of glucose excursion, level and peak and the recovery time in the four-hour postprandial breakfast period.
- To determine the number and percentage of participants who achieved internationally agreed pre and postprandial glucose targets at breakfast time.
- To describe comparisons between all the above measurements and the variables of sex, age, disease duration, BMI, HbA1c, insulin dose/sensitivity and insulin regimen.
- To describe comparisons between all the above measurements and food compositions taken in the breakfast meal.
- To describe comparisons between the above measurements and carbohydrate and insulin adjustments, fluid intake and activities that took place during in the four-hour postprandial breakfast period.

Study design

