This is a descriptive, quantitative study. Dexcom CGM data will be collected retrospectively (for the previous three months) and for the period of recording. Photographic food diaries and answers to morning and evening questionnaire surveys will be collected for seven consecutive days. The morning questionnaire will request information on food and fluids consumed at breakfast as well as insulin management. The evening questionnaire will request information on the four-hour postprandial morning activities in addition to insulin and carbohydrate adjustments and fluid intake. The study duration, commencing with the recruitment of the first participant and ending when data has been fully described, is anticipated to be eighteen months.

Participants

Eligibility criteria

- Children and young people aged between 1-17 years
- Diagnosis of type 1 diabetes for a minimum of one year

- Using multiple daily injections (MDI) together with carbohydrate counting or Continuous Subcutaneous Insulin Infusion (CSII)
- Using Dexcom continuous glucose monitoring (CGM) on a regular basis.
- Access to internet and email

Exclusion criteria

- Prescribed anti-hyperglycaemia agents *i.e.* Glucophage (Metformin) and or antidepressants.
- Have other medical conditions, including complications of diabetes and coeliac disease will be excluded.
- Currently enrolled in another research study

Recruitment

Paediatric diabetes dietitians, working across the UK, will be enrolled to help recruit participants and become principal investigators for their site. On enrolment, the researcher will provide the dietitians with all the relevant participant information sheets and consent forms as well as an Excel spreadsheet for entering the baseline information. The study documentation are presented in Appendices 1-13.

Sample size

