Primary and secondary outcome measures will be based on international guidelines and consensus DiMegloi *et al.* 2018; Battelino *et al.* 2019) of the metrics and target glucose levels to be used in CGM analysis in clinical practice. These are agreed to be:

Metrics:

- Mean glucose
- Glucose variability (GV) % coefficient of variation (COV) target ≤36%
- Time in range (TIR) % and time spent between 3.9-10mmol/I
- Time above target (TAR) % and time spent >10.1-<13.9mmol/l) and >13.9mmol/l
- Time below range (TBR) % and time spent 3.0-3.8mmol/l and <3mmol/l

Target glucose levels:

- TIR % of readings >70% or 16hr 48min
- TAR % of readings <25% or <6hr high and <5% 1hr 12min very high
- TBR- % of readings <4% or <1hr low and <1% or <15min very low

Primary outcome measure:

• Mean glucose (mmol/l) in the four-hour postprandial breakfast period calculated from the CGM measurements at 5 minutes intervals.

Secondary outcome measures – post prandial period:

• Number and percentage who had pre-prandial glucose in target Mean peak glucose level (mmol/l), mean time to peak (mins), mean time to recover (to pre-prandial levels) (mins) in the four-hour postprandial breakfast period

- TIR, TBR and TAR (% and time) in the four-hour postprandial breakfast period
- Comparisons of the above measurements between cohorts and breakfast meal compositions and drinks, snacks taken in the morning and activities and insulin adjustments taken in the 4-hour postprandial period.

Secondary outcome measures – glucose variability:

• TIR, TBR and TAR (% and time) between the hours of 06.00-22.00, 22.00-06.00 and 24-hour period.

Data analysis

This will be a mix of univariate, bivariate and multivariate analysis as this is best suited to describing, summarising and visualising these data. Outputs will include the distribution of glucose levels and diurnal, nocturnal and post-breakfast variability to determine the spread and dispersion of the data. As well as providing new evidence on this phenomenon, it will also assist in determining required sample size for any subsequent investigation including an intervention testing of effects on interstitial glucose levels arising from different food intakes.

Safety considerations

Recruitment/consent

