Consideration will be given to those potential participants/families who are experiencing difficulties managing their condition, for example 'diabetes burnout'; poor glycaemic control or other stressors, for example, family difficulties, stress at school, for example, dealing with bullying or exam pressures. This will be minimised by recruiting via the managing dietitian who will have significant knowledge of the potential participant and who will be expected to discourage recruitment, if it is felt the family have enough to cope with. Those who are newly diagnosed will not meet the eligibility criteria as it is felt this would be unethical given the pressure they will be experiencing dealing with a new diagnosis of a chronic disease. Participants will not be asked to change their usual diabetes management or dietary intake.

Personal data collection

Personal data as described above will be collected and will be securely managed. How this will be managed is described in the 'Data Management' section.

Burden on dietitians

Dietitians, as Principal Investigators, will need to be allowed additional time to recruit participants. Dietitians will be asked to discuss this with their managers and gain their approval for this and also with their diabetes teams.

Burden on families

This is minimised by utilisation of digital technology to ensure that completion of food diaries and questionnaire surveys are not time consuming. Payment for expenses and time may be considered. Funding to support this (from the British Dietetic Association) will be applied for but can only be submitted once ethical approval has been sought and granted.

Data management

Assessment of existing data

There appears to be a dearth of available data on the distribution and dispersal of glucose levels in children and young people who have T1D. Nor does there appear to be any published data comparing glucose measurements from Dexcom CGM with different breakfast compositions in children and young people with T1D. The project is therefore not creating new data when existing data could be re-used.

Creation of new data

This will include the following:

- Retrospective and on-going Dexcom CGM measurements of interstitial glucose
- Baseline information as discussed earlier
- Information and analysis of food and drink intake at breakfast and activities and adjustments in the four-hour postprandial period as discussed earlier.

Methods of anonymisation, pseudonymisation and encryption

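### Mean time to peak has no rule for breakfasts with no rise or still rising at 240 minutes, so read literally it partly measures how common those breakfasts are

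*Combined protocol and SAP*

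**What the plan says.** In the combined protocol and SAP, the post-prandial secondary outcomes under Outcome measures include "Mean peak glucose level (mmol/l), mean time to peak (mins"). The two timing outcomes in that item read in full "mean time to peak (mins), mean time to recover (to pre-prandial levels) (mins) in the four-hour postprandial breakfast period". The same list then calls for "Comparisons of the above measurements between cohorts and breakfast meal compositions and drinks, snacks taken in the morning and activities and insulin adjustments" in that period, so time to peak is one of the quantities to be compared between meals.

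The related item under Objectives is "To determine the variability of glucose excursion, level and peak and the recovery time in the four-hour postprandial breakfast period". It gives no rule for a trace without a turning point. The primary outcome is "calculated from the CGM measurements at 5 minutes intervals", which is the only statement of the reading grid.

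Study design adds that "Photographic food diaries and answers to morning and evening questionnaire surveys will be collected for seven consecutive days", so a child can contribute up to seven breakfasts. The Recruitment/consent text under Safety considerations says "Participants will not be asked to change their usual diabetes management or dietary intake". The Data analysis section names only broad classes of analysis. The distributions it promises are of glucose levels and variability, not of time to peak.

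**The concern.** A closed window from 0 to 240 min always contains a highest reading. Anyone applying the wording as it stands therefore gets a time to peak for every complete trace, including traces with no post-meal peak:

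- If glucose falls from the start, the maximum is at or near 0 min.
- If glucose stays flat, the maximum lies wherever sensor noise puts it.
- If glucose is still rising when the window closes, the maximum is recorded at 240 min and the true peak is unknown.

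Unlike a missing recovery time, these values look valid and would not stand out in the dataset.

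Such traces are plausible in free-living data. The plan counts who starts in the pre-prandial target, so it allows for some who do not. It also expects snacks, activity and insulin adjustments within the four hours. If the shares of these traces differ between groups, the group means differ for that reason alone, and a real difference in peak timing can shrink. This matters because comparing breakfast compositions is a stated objective, and the results are meant to inform the question and sample size of a later trial of breakfasts.

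**Working it through.** **Figure to reproduce.** None. The plan states no value, standard deviation or expected difference for time to peak.

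**Inputs from the documents.** The window is 240 min. With 5-minute readings and both ends counted, that is 240/5 + 1 = 49 readings, so a recorded time to peak lies between 0 and 240. Each child has up to seven breakfasts.

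**Inputs assumed, because the documents give none.** The share p0 with the maximum at time 0, the share pc with the maximum at 240 min, and the mean μ among breakfasts that peak inside the window.

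**Formula.** Mean time to peak = p0 × 0 + pc × 240 + (1 − p0 − pc) × μ.

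**Step 1: same timing, different edge shares.** Fix μ = 90 min.

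- Each 10 points of p0 moves the mean by −0.10 × 90 = −9 min.
- Each 10 points of pc moves it by 0.10 × (240 − 90) = +15 min.
- p0 = 30%, pc = 0 gives 0.70 × 90 = 63 min.
- p0 = 0, pc = 20% gives 48 + 0.80 × 90 = 120 min.
- The edges can cancel: p0 = 25%, pc = 15% gives 36 + 0.60 × 90 = 90 min.

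**Step 2: two meals, falling breakfasts only (pc = 0).** Meal A has μ = 75 and meal B has μ = 105, a true difference of 30 min.

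| p0 in A | p0 in B | Mean A | Mean B | B − A |
|---|---|---|---|---|
| 10% | 10% | 67.5 | 94.5 | 27 |
| 20% | 20% | 60 | 84 | 24 |
| 10% | 20% | 67.5 | 84 | 16.5 |
| 10% | 40% | 67.5 | 63 | −4.5 |

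With no falling breakfasts in A, the difference vanishes when p0 in B reaches 1 − 75/105 = 28.6%. With 10% in A, it vanishes at 1 − 67.5/105 = 35.7%.

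**Step 3: both edges, same two meals.** Shares are p0/pc.

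- 5%/5% in both: A = 12 + 0.90 × 75 = 79.5; B = 12 + 0.90 × 105 = 106.5; difference 27 min.
- A 5%/5%, B 30%/5%: A = 79.5; B = 12 + 0.65 × 105 = 80.25; difference 0.75 min.
- A 5%/15%, B 20%/5%: A = 36 + 0.80 × 75 = 96; B = 12 + 0.75 × 105 = 90.75; difference −5.25 min.

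**Step 4: would excluding the late maxima do?** Suppose true peaks are normal with mean 180 and SD 60 min (assumed). The share beyond 235 min is P(Z > 55/60) = about 18%. The median of those left inside the window is about 167 min instead of 180. Exclusion removes the slowest breakfasts and makes a slow meal look faster.

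**The case against.** The strongest reply is that the protocol is silent, which is not the same as deciding to include these traces. A reader might infer that the plan has chosen to average non-peaks. It has not said so, and an analyst could leave time to peak undefined when glucose does not rise. This stands as a limit on the wording. It does not remove the problem, because the stated summary is a plain mean with no exclusion, and any exclusion would be a rule chosen after the data are seen.

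A reader might also infer that meal comparisons will be hidden or reversed. The documents give no frequencies and so do not support that. At equal 10% shares, 27 of the 30 min survive.

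A third tempting reading is that the outcome exists to measure speed of rise. No section states that purpose, and the Objectives item does not name time to peak. The point here does not depend on it.

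Finally, this is one descriptive secondary outcome with no decision rule. Peak level and pre-prandial status are reported beside it and would partly reveal a group with many falling breakfasts. The 5-minute data also allow the definition to be settled before analysis. All of this stands, and it keeps the point modest.

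**Conclusion.** The concern holds in a limited form. The plan summarises time to peak by a plain mean, compares it between cohorts and meals, and gives no rule for a maximum at either edge of the window. Taken literally, the mean depends on the edge shares as well as on peak timing. With timing fixed at 90 min, it runs from 63 to 120 min over the ranges tried (p0 from 0 to 30%, pc from 0 to 20%).

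For a comparison, the damage depends on how unequal the shares are. It is small when they are small and similar, about half the difference at 10% v 20% falling, and a reversal only at contrasts such as 10% v 40%. All shares and peak times are assumptions, so the size in this study is unknown. Mean four-hour glucose, the primary outcome, is not affected. The change is worth making before analysis, but it does not threaten the study's main result.

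**What to change.** Replace the plain mean with a two-part summary for each cohort and meal group.

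1. Report the percentage of breakfasts with no rise, meaning a rise over the pre-prandial reading below a pre-stated minimum, or the maximum at the first reading. Report separately the percentage with the maximum at the last reading of the window.
2. Among breakfasts that rose, report the median (IQR) time to peak. Treat those with the maximum at 240 min as right-censored, for example with a Kaplan-Meier median, and do not exclude them. If too many are censored for a quartile to be reached, report it as beyond 240 min.

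Compare groups on both parts, with a method that allows for up to seven breakfasts per child, such as intervals from resampling whole children.

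The cost is a few lines of analysis text and no new data. A minimum-rise threshold must be fixed before analysis. Time to peak will then describe only breakfasts that rose, so it must always be shown beside the percentages in part 1.

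### Recovery time is a plain mean within four hours, with no rule for breakfasts that have not recovered by then, so the mean and its comparisons can be distorted

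*Combined protocol and SAP*

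**What the plan says.** Under Outcome measures, the secondary outcomes for the postprandial period include "mean time to recover (to pre-prandial levels) (mins) in the four-hour postprandial breakfast period". The Objectives use the same window: "To determine the variability of glucose excursion, level and peak and the recovery time in the four-hour postprandial breakfast period".

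The measure is meant for comparison. The Objectives include "To describe comparisons between all the above measurements and food compositions taken in the breakfast meal", and the secondary outcomes list "Comparisons of the above measurements between cohorts and breakfast meal compositions and drinks, snacks taken in the morning", followed by activities and insulin adjustments.

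Three neighbouring items bear on it. The same outcome list has "Number and percentage who had pre-prandial glucose in target" and "TIR, TBR and TAR (% and time) in the four-hour postprandial breakfast period", and the Objectives have "To determine the number and percentage of participants who achieved internationally agreed pre and postprandial glucose targets at breakfast time".

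Under Study design, "Dexcom CGM data will be collected retrospectively (for the previous three months) and for the period of recording". The trace may therefore continue beyond four hours even though the outcome stops there.

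The Data analysis section names only univariate, bivariate and multivariate analysis. It mentions no censoring, time-to-event or restricted-mean method. Neither section gives a rule for a breakfast not back at its starting level by four hours, for one that never rises above that level, or for a trace that ends early. Neither states when the recovery clock starts.

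**The concern.** A mean time to recover can be calculated directly only for breakfasts that recover. Those still raised at 240 minutes have the longest recovery times, and the definition gives them no value. The study is built on the premise that high glucose after breakfast is common in these children, so some breakfasts of this kind should be expected. The documents do not say how many.

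If the analyst averages the available times, each group's mean describes a selected subset, and the selection differs between groups whenever the share recovered differs. A meal that delays recovery in many children could then look much like one that does not. Nothing in the planned output would reveal this, because the share recovered is not reported. The protocol also intends the results to help frame and size a later trial of breakfast meals, so a distorted difference could carry forward.

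**Working it through.** **Inputs.** From the documents: the window is four hours, so τ = 240 min. CGM readings are 5 minutes apart (stated for the primary outcome), and breakfasts are recorded on seven consecutive days. The plan gives no recovery time, spread or share recovered, so it has no figure of its own to reproduce. All recovery-time inputs below are assumptions: lognormal times with median m and log-SD s, measured from breakfast, with complete traces.

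**Formulas.**
- z = ln(240/m)/s; share recovered p = Φ(z); M = m·exp(s²/2); A = M·Φ(z − s)
- Recovered-only mean C = A/p
- 240-minute restricted mean R = A + 240(1 − p). This is also what results from entering 240 for every unrecovered breakfast.
- Subtracting, R − C = (1 − p)(240 − C). This is never negative, so the recovered-only mean is never above R and falls below it whenever any breakfast is unrecovered.

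**One case in full (medians 120 v 150, s = 0.4).**
- m = 120: z = 1.733, p = 0.958, M = 130.0, A = 118.1. C = 118.1/0.958 = 123.2; R = 118.1 + 240 × 0.042 = 128.1.
- m = 150: z = 1.175, p = 0.880, M = 162.5, A = 126.9. C = 126.9/0.880 = 144.2; R = 126.9 + 240 × 0.120 = 155.7.
- Differences: 20.9 min recovered-only against 27.6 restricted. Shrinkage = 1 − 20.9/27.6 = 24%.

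**Equal spread in both groups** (differences in minutes, slower minus faster):

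| Medians | s | Recovered by 4 h | Recovered-only | Restricted | Shrinkage |
|---|---|---|---|---|---|
| 90 v 120 | 0.4 | 99.3 v 95.8% | 27.0 | 30.9 | 12% |
| 90 v 120 | 0.6 | 94.9 v 87.6% | 20.1 | 28.1 | 28% |
| 90 v 120 | 0.8 | 89.0 v 80.7% | 15.2 | 24.5 | 38% |
| 120 v 150 | 0.4 | 95.8 v 88.0% | 20.9 | 27.6 | 24% |
| 120 v 150 | 0.6 | 87.6 v 78.3% | 14.8 | 23.0 | 36% |
| 120 v 150 | 0.8 | 80.7 v 72.2% | 11.2 | 19.4 | 42% |
| 150 v 240 | 0.4 | 88.0 v 50% | 35.0 | 53.9 | 35% |
| 150 v 240 | 0.6 | 78.3 v 50% | 26.3 | 43.9 | 40% |
| 150 v 240 | 0.8 | 72.2 v 50% | 21.0 | 37.3 | 44% |

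These cases are not a floor. Medians 60 v 90 at s = 0.4 give 31.3 against 32.3, a shrinkage of 3%, because over 99% recover in both groups.

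**Unequal spread** (median/log-SD):

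| Groups | Recovered-only | Restricted | Effect |
|---|---|---|---|
| 150/0.4 v 200/0.6 | +4 | +28 | nearly removed |
| 150/0.4 v 200/0.8 | −12 | +21 | reversed |
| 150/0.6 v 200/0.4 | +36.1 | +36.1 | unchanged |
| 120/0.6 v 150/0.4 | +27.6 | +23.8 | enlarged |
| 200/0.6 v 260/0.3 | +48.3 | +39.7 | enlarged |

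The last row shows why the direction is not fixed. The shortfall R − C is 183.2 − 148.3 = 34.9 min in the first group (62% recovered) but 222.9 − 196.6 = 26.3 min in the second (39% recovered). The group with fewer recoveries loses less, because those that do recover do so late in the window.

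**Traces that end early.** Suppose 10% of traces end at a uniform time between 0 and 240 minutes, with m = 120 and s = 0.4. By simulation, entering 240 for the lost traces gives a mean of 133.1 against a true restricted mean of 128.1. Kaplan-Meier gives 128.1. The raw percentage recovered is 90.9% against a true 95.8%.

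**The case against.** The plan does not say that unrecovered breakfasts are dropped. Entering 240 for them is equally open, and with complete traces that gives exactly the restricted mean, with no shrinkage against that benchmark. This stands. The established fault is that the rule is missing; the bias depends on which reading the analyst takes. Even the 240 reading needs stating, because its result is a restricted mean and not a mean recovery time.

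A reader might infer that differences between meals always shrink, or that the slowest meals must look closest to the others. The unequal-spread results do not support this: the difference can also be unchanged, enlarged or reversed.

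A reader might also take 12% to 44% as the expected size. It rests wholly on assumed distributions. In the 12% case the two differences are 3.9 minutes apart, less than one CGM reading interval.

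Other outcomes partly cover the gap. Four-hour mean glucose and time above range reflect prolonged rises without any recovery rule, and the target counts add something. The cover is incomplete. Time above range uses fixed thresholds, whereas recovery is relative to each breakfast's own starting level: a lasting rise from 5 to 9 mmol/l adds nothing to time above range. None of these outcomes gives the share recovered.

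Finally, this is a descriptive study with no stated hypothesis test, and its page footer calls the text a protocol summary, so some missing operational detail is unsurprising. That lowers the severity but does not supply the rule.

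**Conclusion.** The point holds at minor severity. The recovery outcome gives no value to a breakfast not recovered by 240 minutes, and the plan neither handles such breakfasts nor counts them. If they are omitted, the mean is biased low whatever the distribution. Comparisons are then distorted, usually towards zero when groups have similar spread, with no fixed direction otherwise.

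The size cannot be taken from the documents. It depends on the share unrecovered and the spread of recovery times, neither of which is given, and it is small if nearly all breakfasts recover. The documents do not support reading this as a threat to the study as a whole: the primary outcome, mean glucose over the four hours, does not use recovery time.

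**What to change.** In the secondary outcomes for the postprandial period, replace the plain mean with: time from the start of breakfast to first return to the pre-prandial level after a rise, censored at 240 minutes, or at the last CGM reading if earlier. If the clock is meant to start at the peak, say so and adjust the limit, which is then 240 minutes less the time to peak.

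Then specify:
- **Summaries:** the number and percentage recovered by four hours, the Kaplan-Meier median where reached, and a mean labelled as a 240-minute restricted mean. Take the percentage and the restricted mean from the Kaplan-Meier curve, so that traces ending early are not counted as 240, and report how many such traces there are. This assumes that early ending is unrelated to recovery.
- **Comparisons:** use these summaries between cohorts and meals, with intervals that allow for up to seven breakfasts per child, for example a bootstrap that resamples children.
- **Breakfasts that never rise above the pre-prandial level:** report them as a separate count and leave them out of the recovery-time curve.

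The cost is a few lines of wording and a little more analysis, with no new data. The restricted mean says nothing about differences after four hours.

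### Meal-composition comparisons of absolute post-breakfast glucose specify neither adjustment for that breakfast's pre-prandial glucose nor handling of repeated breakfasts, and the excursion named in the second objective has no listed outcome

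*Combined protocol and SAP*

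**What the plan says.** The primary outcome is "Mean glucose (mmol/l) in the four-hour postprandial breakfast period calculated from the CGM measurements at 5 minutes intervals". The secondary post-breakfast outcomes add the peak, time to peak, and time in, below and above range. They use the pre-meal value in two ways only: "Number and percentage who had pre-prandial glucose in target" and "mean time to recover (to pre-prandial levels) (mins) in the four-hour postprandial breakfast period".

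The same list then includes "Comparisons of the above measurements between cohorts and breakfast meal compositions and drinks, snacks taken in the morning", and it extends the comparison to "activities and insulin adjustments taken in the 4-hour postprandial period". The method given in Data analysis is: "This will be a mix of univariate, bivariate and multivariate analysis as this is best suited to describing, summarising and visualising these data". No covariate, unit of analysis (child or breakfast) or correlation structure is named. Pre-prandial glucose is not among the participant variables that the Objectives list for comparison.

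Study design has breakfasts recorded on seven days in a row. Safety considerations says that usual diet and diabetes management are left alone, so meals are self-chosen. The second objective is "To determine the variability of glucose excursion, level and peak and the recovery time in the four-hour postprandial breakfast period"; the outcome list as it can be read has no excursion measure. On later use, Data analysis says that "it will also assist in determining required sample size for any subsequent investigation", and Expected outcomes names a breakfast intervention trial.

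**The concern.** The four-hour mean, the peak and the range percentages come from a trace that begins at the pre-prandial value, so they partly record where the child started. Meals are not assigned. If a child eats differently on mornings when glucose is already high, an unadjusted comparison by meal composition attributes some of the overnight control to the food. Recovery time is less exposed, because it is already referenced to the pre-prandial level.

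Pre-prandial glucose is measured before eating. The activities and insulin adjustments that the plan also compares fall after the meal and may be consequences of it.

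Up to seven breakfasts from one child are not independent observations, and a standard error that ignores this is wrong. Expected outcomes makes the nutrient comparisons a stated output and hopes to base a power calculation on the results, so both points bear on what the study is for. The missing excursion outcome is smaller: part of one objective has nothing listed to report it.

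**Working it through.** Inputs from the documents: a 4-hour window and 5-minute readings (Primary outcome measure), seven breakfast days (Study design), about 435 participants (Sample size). The documents give no SD, intraclass correlation (ICC), carry-over of starting glucose, or relation between starting glucose and food choice. All such values below are assumptions.

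1. The plan's own sample size. 29,000 × 0.18 = 5,220 patients; 5,220 × 0.11 = 574 (plan: 572). 180 × 0.18 = 32.4 dietitians; 435 / 32.4 = 13.4 each, within the stated 13-14. The 435 reproduces as a workload figure, so it supplies no variance with which to size this point. It allows at most 435 × 7 = 3,045 breakfasts.

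2. Units. 240 / 5 = 48 readings per window; 100 / 48 = 2.1 percentage points each. These are the only assumption-free figures here. As illustration, a breakfast that starts above 10 mmol/l and is assumed to take 30 or 60 minutes to come down has 6 or 12 readings above range, that is 12.5 or 25 points, before any food effect.

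3. Carry-over to the 4-hour mean (assumed shapes). A starting difference that fades linearly to zero over T minutes contributes b = T / (2 × 240) of itself. T = 120, 180 or 240 gives b = 0.25, 0.375 or 0.5. If half remains at 4 hours, b = (1 + 0.5) / 2 = 0.75.

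4. Spurious meal slope. Assume a within-child SD of 2.5 mmol/l for pre-prandial glucose (variance 6.25) and 10 g for carbohydrate (variance 100), no true food effect, and k g less carbohydrate eaten per extra mmol/l. The slope per 10 g is −10 × b × k × 6.25 / 100:

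| b | k = 0.5 | k = 1 | k = 2 |
|---|---|---|---|
| 0.25 | −0.08 | −0.16 | −0.31 |
| 0.5 | −0.16 | −0.31 | −0.63 |
| 0.75 | −0.23 | −0.47 | −0.94 |

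Eating more instead of less reverses every sign; k = 0 gives zero.

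5. Excursion. If peak = a + β·meal + γ·pre + error, then peak − pre = a + β·meal + (γ − 1)·pre + error. With pre-prandial glucose in the model, the meal coefficient is β for both. Without it, b is replaced by b − 1: with an assumed peak carry-over of 0.4 or 0.7 and k = 1, the spurious slope is +0.38 or +0.19, opposite in sign to that for an unadjusted level.

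6. Repeated breakfasts. Design effect = 1 + (7 − 1) × outcome ICC × meal ICC. For a meal habit fixed within the child (meal ICC 1), assumed outcome ICCs of 0.1, 0.3 and 0.5 give 1.6, 2.8 and 4.0, so the true standard error is 1.26, 1.67 or 2.0 times the naive one. At meal ICC 0.3 the design effects are 1.18, 1.54 and 1.90. For composition fully balanced within child (meal ICC −1/6) the design effect is 1 − outcome ICC, and the naive standard error is too wide.

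7. SD for later planning. Assume between/within SDs of 1.66/2.5 for pre-prandial glucose and 1.2/2.0 for the residual outcome. Adjusted total variance = 1.44 + 4 = 5.44 (SD 2.33). Raw total variance = 5.44 + b² × (1.66² + 6.25), so the SD is 2.45 at b = 0.25 and 3.24 at b = 0.75. The raw-to-adjusted variance ratio is 1.10 to 1.93. Within child it is (4 + b² × 6.25) / 4 = 1.10 to 1.88.

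**The case against.** The study is descriptive. It sets no hypothesis test and no alpha, its objectives are to describe comparisons, and an unadjusted comparison is a valid description. The multivariate analysis it plans could include pre-prandial glucose and a child effect. Analysing one average per child would avoid the clustering problem. Read literally, the outcome list even compares the pre-prandial in-target count across meals, which could reveal an imbalance in starting level. Breakfast insulin dose, collected in the morning survey, may respond to both starting glucose and carbohydrate, so a model with one covariate does not settle confounding. Recruitment has been slow and some participants supply CGM data only, so the 3,045 is a ceiling and small biases could be lost in noise.

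Most of this stands as a limit on the point. It does not remove it. Permission to adjust is not a specification, and steps 4 and 5 show that unadjusted levels and unadjusted change scores can err in opposite directions, so the choice should be fixed beforehand. Averaging per child loses the link between each breakfast and its response. An in-target count shows imbalance without correcting for it. The insulin point is right and is taken into the fix.

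A reader might infer that the meal comparisons are biased, or that error rates are inflated. The documents support neither: they do not relate food choice to starting glucose, and they set no test whose error rate could be inflated. A reader might also infer that the absolute four-hour mean is the wrong primary outcome; for the descriptive aim it is valid.

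**Conclusion.** The point holds as a gap in the specified analysis with a better method at hand; it is not an arithmetic error. As written, the plan compares measures that partly reflect starting glucose across self-chosen meals, without stating how starting level or repeated breakfasts are handled.

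The size of any bias is unknown. Only the 48 readings and 2.1 points per reading rest on the plan alone. The range of 0.08 to 0.94 mmol/l per 10 g, in either direction, depends on the assumed SDs, carry-over and k, and the bias is zero if food choice is unrelated to starting glucose. The design effects depend on assumed ICCs. The variance ratios also assume that the later trial adjusts for baseline, which the documents do not state.

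The excursion gap is one of wording: the peak and pre-prandial values are both already in use. The outcome list runs two items together at that place, so confidence that excursion was truly omitted should be modest. The change should be made; confidence is medium.

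**What to change.** 1. In Data analysis, state that breakfast-level meal-composition comparisons of the four-hour mean and peak use a mixed model with that breakfast's pre-prandial CGM glucose as a continuous covariate and a participant random effect, reported beside the unadjusted result. For time in, above and below range, use the same covariate with standard errors clustered by child and a method suited to percentages, such as fractional logit. Limit this to participants with breakfast data. Describe it as adjustment for starting glucose only, and show results with and without breakfast insulin dose as a sensitivity analysis.
2. List excursion (peak minus pre-prandial glucose) as a descriptive secondary outcome. No separate adjusted meal comparison is needed, because its meal coefficient equals that for peak.
3. Keep comparisons by HbA1c, regimen and other participant characteristics unadjusted as the main description, since pre-meal glucose may lie on the pathway. The primary outcome also stays unadjusted.
4. Report the SD of the four-hour mean split into between-child and within-child parts, raw and baseline-adjusted, for the later trial's sample size.

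The cost is plan wording, one added outcome and slightly more analysis. The four-hour window, in-target count and recovery time already presuppose a meal-start time and a pre-prandial value. The questionnaires are not in the reviewed text, so how meal start is recorded could not be checked. Breakfasts with a sensor gap just before the meal drop out of the adjusted comparison; the unadjusted result beside it can retain them.
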